10.1.1 Cluster-randomized controlled study (Phase 1)

For the cluster-randomized study in Phase 1, the primary analysis will evaluate whether the use of ePOCT+ for case management of sick children in PHC facilities 1) results in similar clinical cure at day 7 (non-inferiority analysis), as compared to routine care and 2) decreased antibiotic prescriptions (superiority analysis) at the initial consultation. The sample size was calculated for testing the non-inferiority of the clinical cure outcome, which will require a much larger sample size due to the rareness of the event. In addition, the testing of differences in antibiotic prescription is conditional on satisfying non-inferiority in the clinical outcome. Assuming a failure rate of 3% in the control arm (corresponding to a 97% clinical success rate), based on previous studies, the acceptable non-inferiority margin will be a risk ratio of 1.3. This corresponds to the upper bound of the difference in failure rate not exceeding 0.9% if the control group failure rate is 3%. We utilized a fixed risk ratio rather than an absolute risk difference to protect against potential unexpected event rates (Head et al. 2012).

We assumed a cluster size of 900 patients and an intraclass correlation coefficient of 0.002 in the clinical outcome based on similar studies. To have 80% power to detect a risk ratio 1.3, for a one-sided hypothesis test at alpha of 0.025, we would require 19 clusters and 17,100 patients per arm (total patients n=37,620 assuming 10% loss to follow-up), rounded to a total of 40 HFs and 40'000 patients. However, due to uncertainty regarding the assumptions of the sample size calculation and to capture a wider more representative range of conditions, we will continue recruitment for Phase 1 for a minimum of 6 months. Due to lower enrollment than initially anticipated, an independent statistician will use the clinical failure outcome data from the control arm, and projected number of patients enrolled after all health facilities have enrolled patients for a minimum of 6 months to recalculate the sample size. If the sample size recalculation does not have sufficient power to meet the study objectives, the study may be extended, or the number of health facilities increased. To avoid implementation bias, the clinical failure proportion in the control arm will not be shared to the study team.

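### The 80% power stated for the Phase 1 risk-ratio margin of 1.3 is about 69–72% at 19 clusters per arm when computed on the risk-ratio scale from the protocol's own inputs

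*Protocol*

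**What the plan says.** Protocol section 10.1.1 sets the margin on the ratio scale: "the acceptable non-inferiority margin will be a risk ratio of 1.3". It gives the reason: "We utilized a fixed risk ratio rather than an absolute risk difference to protect against potential unexpected event rates". It then translates the ratio into a difference, conditionally: "This corresponds to the upper bound of the difference in failure rate not exceeding 0.9% if the control group failure rate is 3" per cent. The planning inputs are "Assuming a failure rate of 3% in the control arm" and "We assumed a cluster size of 900 patients and an intraclass correlation coefficient of 0.002". From these it concludes "To have 80% power to detect a risk ratio 1.3, for a one-sided hypothesis test at alpha of 0.025, we would require 19 clusters". This amounts to 17,100 children in each arm, a number it inflates for 10% loss and rounds to 40 facilities and 40,000 patients.

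The section gives no formula and no assumed true failure rate in the intervention arm. It also plans a recalculation by an independent statistician, using control-arm failure data and projected enrolment, without naming a scale or method.

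Section 10.3 says that a confidence-interval approach will be used for non-inferiority, again without naming the scale. Both sections make the antibiotic comparison conditional on non-inferiority. The synopsis gives the same 19 clusters and 17,100 patients, but with an absolute margin of 1%. The SAP supplied covers the Phase 2 medAL-mentor study and does not deal with this analysis.

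**The concern.** A margin of 0.9 percentage points and a margin of 1.3 on the ratio coincide only when the control failure rate is known to be 3%. In the trial that rate is estimated. A test against a ratio of 1.3 therefore carries the sampling error of the control rate multiplied by 1.3, and needs more information than a test against a fixed 0.9-point difference. This would be so even with equal clusters, full follow-up and exactly 3% failure.

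Non-inferiority is the gate for the antibiotic co-primary. If power is about 70%, the chance of failing the gate when the arms are truly equal is about 30% rather than the planned 20%, and the antibiotic claim fails with it. The scale also matters for the recalculation, because a difference-scale calculation gives a more favourable power than the declared margin supports.

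**Working it through.** **Inputs** (all from section 10.1.1 unless noted)
- Control failure p = 0.03; margin RR = 1.3, or 0.009 as a difference at 3%.
- One-sided alpha 0.025 and 80% power: (1.960 + 0.842)² = 7.849.
- m = 900 and ICC = 0.002: design effect 1 + 899 × 0.002 = 2.798.
- True RR = 1, so 3% in both arms. *This is an assumption; the protocol states no true effect.*

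**Step 1. Reproduce the stated 19**

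Fixed difference of 0.009:

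n = 7.849 × 2 × 0.03 × 0.97 / 0.009² = 5,640 per arm. Times 2.798 this is about 15,780, or 17.5 clusters of 900.

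Adding one cluster as a small-sample allowance gives 18.5, so 19. Alternatively, with a t reference on 2(K − 1) degrees of freedom, power is 78.7% at 18 clusters and 81.0% at 19, so 19 is the smallest number that reaches 80%. With a normal reference, power at 19 is 83.1%.

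The other standard calculations tried do not return 19:

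| Calculation | Clusters per arm |
|---|---|
| Absolute margin 1% | 14.2 (15, or 16 with one added) |
| 3% vs 3.9%, pooled variance | 20.1 (20.8 with continuity correction) |
| 3% vs 3%/1.3 | 26.3 |
| Log RR against ln 1.3 | 22.9 |
| Score test of RR = 1.3 | 23.0 |
| Contrast p1 − 1.3 p0 | 23.6 |

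**Step 2. Size on the declared scale**

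Log RR: n = 7.849 × 2 × (0.97/0.03) / (ln 1.3)² = 7,374 per arm. Times 2.798 this is 20,631, or 22.9 clusters.

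Contrast p1 − 1.3 p0: the variance factor is 1 + 1.3² = 2.69 instead of 2, so n = 7.849 × 2.69 × 0.03 × 0.97 / 0.009² = 7,585. Times 2.798 this is 21,223, or 23.6 clusters.

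**Step 3. Power at the stated size** (19 × 900 = 17,100 per arm)

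SE(log RR) = √(2 × (0.97/0.03) × 2.798 / 17,100) = 0.1029. Then ln 1.3 / SE = 0.2624 / 0.1029 = 2.55, and power = Φ(2.55 − 1.96) = 72%.

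| Clusters × 900 per arm | Log RR, z | Log RR, t | Contrast, z | Contrast, t | Fixed 0.9-point difference, z / t |
|---|---|---|---|---|---|
| 19 | 72.3% | 69.9% | 71.0% | 68.7% | 83.1% / 81.0% |
| 20 | 74.4% | 72.2% | 73.2% | 71.0% | 84.9% / 83.0% |
| 23 | 80.1% | 78.4% | 79.0% | 77.2% | 89.4% / 88.1% |
| 24 | 81.8% | 80.1% | 80.7% | 79.0% | 90.6% / 89.4% |

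A beta-binomial cluster simulation (100,000 runs) gave 72.2% (z) and 69.9% (t) for log RR at 19 clusters, in agreement with the formulas. Even 20 clusters of 1,000 evaluable children give only 73–76% on the ratio scale.

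**Step 4. The synopsis margin**

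Against a fixed difference of 1%, 19 clusters give about 90% (z) or 88% (t). The ratio-scale figure therefore cannot be placed beside the synopsis margin as it stands.

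**The case against.** The arithmetic is hard to dispute, but four points on the other side deserve weight.

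**The cause is not documented.** No formula appears, the plain difference formula gives 17.5 rather than 19, and the synopsis attaches the same 19 to another margin, so the number may have been carried over. This stands. The fixed 0.9-point difference is the best-fitting explanation, not an established one. The shortfall does not depend on it, because no ratio-scale method tried reaches 80% at 19 clusters.

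**The inputs are uncertain, and modest changes restore 80% at 19 clusters.** On log RR, any one of these would do it: a control failure rate of about 3.6–3.8%, a true ratio of about 0.96–0.97, or an ICC of about 0.0013–0.0015. The earlier trials described in section 1.6 report routine-care cure of 95% and 92%; at 5% failure, power would be about 90–91%. This stands against any claim that the trial is bound to be too small. It does not rescue a power statement made for 3% and 0.002.

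**The recalculation is a safeguard.** A reader might infer that it would repeat the difference-scale calculation. The protocol does not support that: the method is not given and the work is assigned to an independent statistician. What can be said is that the scale is unspecified and that a difference-scale calculation would overstate power.

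**Low power does not create a false safety claim.** A reader might go further and infer that 0.3 times the observed control rate will be treated as a known margin, inflating the type I error. Nothing in the documents proposes this. Section 10.1.1 fixes the margin as a ratio, section 10.3 plans a confidence interval, and section 10.3 defers detail to an analysis plan; the Phase 1 SAP is not among the documents supplied.

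**Conclusion.** The concern holds for the stated figure. For a risk-ratio margin of 1.3, the design in section 10.1.1 has about 69–72% power at 19 clusters of 900 per arm and 71–74% at 20, not 80%. On log RR, 80% takes 23 clusters per arm (normal reference) or 24 (t reference), about 20,700–21,600 evaluable children per arm against 17,100 stated. Rounding up to 20 facilities per arm recovers only 2–3 points.

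This rests on the protocol's 3% failure rate, ICC of 0.002 and equal clusters of 900, and on the assumption of a true ratio of 1. A higher control failure rate, a lower ICC or a real benefit would raise the power. The finding is that the stated power does not match the stated margin; it does not show how the error arose, that the trial will fail, or that its error rate is inflated.

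**What to change.** - **Section 10.1.1.** Restate power for a ratio of 1.3 as about 70–72% at 19 clusters and 71–74% at 20 clusters per arm with 900 evaluable children each. Give the formula, the reference distribution and the assumed true ratio.
- **Sections 10.1.1 and 10.3.** State that non-inferiority is read from the confidence interval of the risk ratio, compared with 1.3.
- **Recalculation.** Specify that the independent statistician uses the variance of log RR, or of p1 − 1.3 p0. SAP section 2.1 already reports preliminary Phase 1 findings, so if the recalculation has been done, report which scale was used.
- **Synopsis.** First align the 1% absolute margin with the ratio of 1.3, then carry over the same power figure. Inserting the figure beside the 1% margin would create a new contradiction.

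The cost is wording and one recalculation, and a less favourable stated power. Correcting the figure requires no added patients. Whether to extend the study or add facilities remains the decision that section 10.1.1 already provides for, and it should be made on the ratio scale.

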10.1.2 Randomized sub-studies to test algorithm modifications (Phase 2)

Sample sizes for the randomized sub-studies aimed at evaluating the benefit of a modification in an algorithm branch will be calculated following the same general principles as for Phase 1. Consideration of the desired or acceptable difference in clinical cure rate will be determined according to the type of intervention applied. This acceptable difference cannot be decided prior to knowing what intervention will be implemented, and on which population or subpopulation this intervention will be applied. For example, a small improvement in the cure rate from 90% to 93% in a certain sub-population of patients will be considered beneficial if not too demanding in terms of resources to be added. The same considerations will be applied for interventions aiming at improving the rational use of medicines (e.g. antibiotics or antimalarials). The highest sample size between that required for assessing the clinical outcome and that for the resource saving outcome will be used.

10.2 Estimated number of beneficiaries

In Phase 1, the number of direct beneficiaries include children in the intervention arm of the study (n=17,100) and HCWs using ePOCT+ (n=75) for a total of 17,175 people. Indirect beneficiaries may include caregivers and immediate family members who are less exposed to infectious diseases as a result of better cure rates of their child/sibling. Using an average rural household size of 5 people according to the 2004-2005 Demographic and Health Survey, the number of expected indirect beneficiaries is approximately 68,400 (i.e. 4*17,100, excluding the sick child who is a direct beneficiary).

In Phase 2, we expect that an average of 200 children per month per HF will be managed using ePOCT+, which corresponds to around 500,000 consultations over 2 years in the 100 HFs. The number of direct beneficiaries will be less than this, because children may come to the facility more than once, either for the same illness or a different illness over the 2-year study period. In Phase 2,

approximately 300 HCWs are expected to directly benefit from using ePOCT+ and their clinical decision support and e-learning functions. Additionally, approximately 20 users of medAL-monitor and 30 users of medAL-outbreak at the district and national levels will also benefit directly. Lastly, all individuals who are capacitated IT systems management, ML, adaptation of the algorithm through MedAL-Creator, etc. will be included as direct beneficiaries (n=50). Because of high coverage of the intervention in phase 2, indirect beneficiaries will be the entire population of the intervention districts (n=1,053,000) as a result of 1) less exposure to infectious diseases due to better cure rates of sick children; 2) reduced drug pressure and likelihood of antibiotic resistance due to reduced antibiotic prescriptions; and 3) reduced risk of illness due to more effective outbreak detection and response.

10.3 Statistical analyses for the primary outcome measures in the cluster randomized controlled study of Phase 1

Analyses will follow CONSORT guidelines (Schulz et al. 2010, Piaggio et al. 2012) and intention-to-treat (ITT) principles, that is including all participants as randomized. A flowchart will describe the inclusion and follow-up of participants by study arm. Baseline characteristics will be described by study arm with summary statistics such as median and interquartile range or number and percentage; no formal testing between arms will be performed (Pocock et al. 2002). Outcomes will be described by arm using summary statistics. For the non-inferiority comparison between ePOCT+ and the control arm for clinical cure, a CI approach will be used. A figure illustrating the CIs and the non-inferiority margin will be presented. Primary analyses for the non-inferiority comparison will be performed on both the per protocol and ITT sets (Committee for Proprietary Medicinal P 2001). If ePOCT+ is found to be non-inferior to the control in terms of clinical cure rate, then we will assess for superiority using the ITT set. If non-inferiority is established, we will test for significant differences in the co-primary outcome of antibiotic prescription rate. For this outcome, the percentage of patients receiving antibiotics at day 0 will be assessed using multi-level logistic regression model regression with the cluster included as a random effect. Binary secondary outcomes will be evaluated in the same way. All estimates will be reported with 95% confidence intervals (CI).

Effect modification of the primary outcome of antibiotic prescription of the primary endpoints will be performed in groups of patients where the highest reduction in antibiotic prescription is expected, and areas of extension of the content of the algorithm compared to the version tested in the previous ePOCT study. Effect modification by sex, age groups (young infants ages 1 to 59 days, children aged 2 months to 5 years, and children aged 5 to 14 years), respiratory symptoms, fever without clinical source, gastrointestinal complaints (vomiting and diarrhea), skin problems, ear and throat problems, anemia, and malnutrition will be assessed by incorporating an interaction between arm and the respective variable, acknowledging that power will be low. All models will be adjusted for clustering and the stratification factors (Kahan et al. 2012). Primary analyses will be complete case; we may adjust for further baseline variables which are associated with missing outcome data (which is analogous to performing multiple imputation in the case of a single endpoint). Further details will be provided in the statistical analysis plan.

10.4 Machine learning analyses

Machine learning (ML) is a specialized branch of statistics that creates updatable algorithms, which learn from evolving data in real time. Phase 2 of this project will make use of a specially designed algorithm-building platform, that will help clinicians explore and visualize patterns in the data collected by ePOCT+ during phase 1. Two main types of ML methods will be used: 1) Supervised classification and correlation and 2) anomaly detection. The former aims to create algorithms that predict the value of a labeled feature (e.g. the result of a malaria rapid test) using alternative data. Anomaly detection, on the other hand aims to find unusual clusters of values for a certain place, time or person, and are the basis of outbreak detection and discovering erroneous data inputs that could be used to train field workers.

10.4.1 Supervised classification and correlation

Using the insights gleaned from visualizing the data, the expert clinician group will lead the generation of clinically supervised modifications to the static algorithms in ePOCT+ that aim to 1) reduce resource consumption (e.g. predicting the results of expensive or unavailable diagnostic tests), 2) improve or personalize diagnostic accuracy (e.g. creating algorithms adapted to local epidemiology, or better identifying patients who had severe outcomes in phase 1) or 3) improve the completeness of data collected by asking questions that would better predict the values that are missing. For this, the algorithm building platform will allow clinicians to explore various predictive methods, ranging from logistic regression, neural networks and random forests. They will control the inputs required to make the prediction and decide at what threshold the predicted result will impact care decisions. The algorithm will then be updated with accumulating data to best reflect its dynamic environment.

10.4.2 Anomaly detection

Various methods allow us to identify and visualize clusters of abnormal data, by highlighting these instances, clinicians and epidemiologists can train the algorithms by labeling which are of interest and what, if any, actions should be taken when they are detected. Various methods will be explored for this aim and adapted to the type of anomaly under investigation (for example unsupervised density-based approaches such as isolation forests, and k-nearest neighbors [KNN] or multidimensional non-linear kernel-based techniques such as self-organizing maps [SOM] and support vector clustering [SVC]). The clusters deemed interesting will then be investigated for gold-standard labeling by clinicians and the surveillance team and visualizations may be exported to users of the tool for training purposes (medAL-monitor).

10.5 Analyses of data from operational research studies

Quantitative data from cross-sectional quality of care surveys, provider clinical competency or knowledge assessments, and caregiver and patient interviews will be analyzed using conventional statistical methods to compare means (t-tests or paired t-tests) or frequencies (chi-square tests) across intervention groups or time periods. Regression analysis may also be used to explore associations of multiple predictors with outcomes of interest.

All interviews and focus-group discussions will be audio-recorded with the participant's informed consent. Detailed notes will be taken during the interviews. Records will be manually transcribed in its original language (Kiswahili) and translated into English. A qualitative data analysis software (e.g. Nvivo) will be used to code the English interview transcripts in order to identify emerging themes. A predefined list of codes based on the interview guide and the recurrent themes highlighted in the detailed notes will be used. New codes will be created when new themes are identified during more detailed analysis of the transcripts. Deductive coding will be used to extract the themes based on the interview guide, but inductive coding will also be used to extract any unexpected themes that arise during the interviews.

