|--|--|

| | |
|------------------------------------|---|
| | 
 - Carbon footprint of the intervention or carbon-saving due to the intervention |
| Procedures and measurements | 
Objective 1: Improve the integrated management of sick children
 
In Phase 1, in each region, after a pilot period of 6 months to test all the e-tools, eligible HFs will be randomized (by Region and HF) to the intervention or control arm. Sick children will be enrolled over a period of 6 to 9 months.
 
Primary outcome measures: (i) For assessing clinical cure at Day 7, a simple questionnaire (asking if the child is still sick, was hospitalized secondarily, or died) will be administered to all caregivers by phone; (ii) For measuring antibiotics prescribed at initial consultation, the treatment data recorded in the tablets or PCs by HCWs throughout the study will be compared between intervention and control arms.
 
Secondary outcome measures: To determine the quality of the consultation made by CHWs, including the rational use of antimicrobials (antibiotics and antimalarials), two sources of data will be used and compared between intervention and control arms:
 
 - the final decision on referral, tests performed, final diagnoses retained and treatment prescribed will be recorded in the tablets or PCs by HCWs at initial consultations and re-attendance visits. - during a cross-sectional survey, observers in the consultation room will record key symptoms and signs assessed by HCWs, diagnostic tests requested, final decision on referral, final diagnoses retained and treatment prescribed. 
Control arm: In control PHC facilities, sick children will be assessed, diagnosed and treated as per routine protocols by clinicians. A similar but simplified tablet or PC application will also be used in control facilities, but only to record outcome measure related data using an electronic case report form. HCWs in control facilities will be offered the usual training and supervision proposed by the CHMT.
 
In Phase 2, all selected HFs in the two regions will receive the intervention. Indicators monitored over time and across geographical areas will be measured the same way as in Phase 1, except that clinical cure, secondary hospitalizations and deaths may or may not be assessed through a phone call or an automated SMS or call to caregivers using the same simple questionnaire.
 
Objective 2: Improve the algorithm and adapt it to spatiotemporal variations
 
The algorithm will be improved in terms of diagnostic and prognostic accuracy and adapted to local fluctuations in epidemiology, demography, geography and resource availability. These modifications will be designed and supervised by clinical experts, based on accumulated data captured during the study in real-time and analyzed, including by ML when necessary. All modifications will first be tested on retrospectively collected data. If these analyses confirm an expected positive impact, the change in the algorithm will be implemented and its impact will be monitored through the continuous analysis of data looking at the related outcome indicators. For major modifications in the algorithm, a formal randomized sub-study will be conducted to assess precisely the potential benefit (or harm) on clinical outcome or non-inferiority. HCWs attending a child who could potentially benefit from this modification will be informed about the change in the algorithm. Either the modified branch or the standard branch of the algorithm will then appear on the screen to guide the HCW's decisions. Antimicrobial prescriptions, clinical cure and other outcomes related to the expected impact will be assessed the same way as in Phase 1 and compared between children managed with the new and the standard version of ePOCT+. If the positive impact is confirmed by the sub-study, the new algorithm branch will be implemented for all relevant children in the relevant HFs. Minor modifications in the algorithm (e.g. adding a non-critical symptom such as myalgia, or a slight modification of threshold of a laboratory test) will be implemented without sub-study, but some outcome indicators may be monitored.
 
Objective 3: Enhance disease surveillance and outbreak detection
 
All data generated by ePOCT+ will be sent to a central sever based at IHI. Data will be visualized through the medAL-outbreak dashboard made available to district health authorities using the key indicators they will have chosen. To enhance disease
 |

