The purpose of Phase 1 is to compare the effect of using ePOCT+ with routine case management of sick children on the rational prescription of antibiotics, while ensuring a favorable clinical outcome. To date, a prior version of the ePOCT tool was assessed in conditions closer to that of an explanatory trial (Keitel et al., 2017). The present study is designed as a pragmatic randomized controlled study to assess the safety and impact on antibiotic prescriptions of implementing ePOCT+ (including its associated POC tests), supported by initial and continuous training and targeted supervision of health workers, in children attending Tanzanian primary health care facilities. The study will be implemented in settings of targeted future use and involving routine health care personnel, and include all sick children (except those coming for a follow-up visit in the context of a chronic condition). ePOCT+ provides support to HCWs in managing these sick children. Since the intervention takes place at the health provider level and that their practices are influenced by the context of the HF they are working in, randomization at HF level rather than at HCW level or at individual patient level was chosen.

3.2 Phase 2: scale-up of the intervention to 100 health facilities and transformation into a dynamic algorithm

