3.4.1 Cross-sectional quality of care surveys

Before the start of phase 1, during the second half of phase 1, and around 6 months after the beginning of phase 2, three cross-sectional surveys in a subset of randomly selected HFs will be performed to assess the quality of the consultation done by HCWs and their level of compliance to the algorithm (and thus to guidelines). Among the 40 HF included in Phase 1, 18 HF (10 in Morogoro and 8 in Mbeya, half of them being intervention HF and the other half control HF) will be randomly selected. Observers will be trained to attend and observe (without interfering) 25 consecutive consultations with children aged 1 day to 14 years per HF, thus a total 450 HCW/child pairs. Changes over time will be assessed during the three cross-sectional surveys. Before-and-after intervention analysis will be performed between the baseline analysis and the phase 1 intervention arm HF, as well as between the control arm HF in phase 1 and those same HF that will then use the ePOCT+ tool in Phase 2. For the 9 intervention HF, this will provide another way (besides data recorded through the ePOCT+ tool) to measure potential improvement in the quality of the consultation over time. The tools for the quality of care surveys can be found in **Appendix 1**.

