These measures or indicators include the evaluation of the effects of the use of ePOCT+ (versus routine care in Phase 1; over time and across geographical areas in Phase 2) for managing sick children aged under 15 years presenting to PHC facilities on:

Unscheduled secondary consultations:

- % of children with one or more unscheduled re-attendance visits at any HF by day 7

Severe outcome by day 7:

- % of children with non-referred secondary hospitalization by day 7
- % of children who have died by day 7

Primary referrals:

- % of children referred to hospital or admitted to inpatient ward at a health centre at initial consultation
- % of children who were hospitalized among those referred (i.e. referral completed)

Appropriate case management for malaria at initial consultation

- % of febrile children tested for malaria
- % of malaria positive children prescribed an antimalarial
- % of malaria negative children prescribed an antimalarial
- % of untested children prescribed an antimalarial

Appropriate case management for other conditions at initial consultation

- % of key symptoms and signs checked and diagnostic tests performed by HCWs
- Distribution of final diagnoses (including their severity) made by HCWs
- Concordance between treatment prescribed and final diagnoses made by HCWs
- Concordance between final diagnoses as proposed by ePOCT+ and final diagnoses by HCW (*intervention HFs only*)

Definitions used for the outcome measures and indicators of objective 1

- Clinical cure is a positive answer to the question “Is the child cured?” OR “Has the child improved?” (if not cured) asked to caregiver through a phone call (or home visit) at day 7. Non-referred secondary hospitalizations (see definition below) will however be considered as clinical failures even if the child is already cured at day 7.
- Initial consultation is the first visit of a sick child for an acute problem at a HF participating in the study (and thus registered electronically); timeframe from completion of the initial visit up to midnight of the same day.
- Re-attendance visit is a consultation (not necessarily at a HF participating in the study) taking place from the day after initial consultation up to day 7 included. A re-attendance visit can be scheduled (proposed by the HCW on a certain day) or unscheduled (upon decision by caregivers).

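### Protocol 10.5 plans t-tests and chi-square tests on the quality-of-care surveys with no allowance for the health facility, which is the randomised unit

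*Protocol*

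**What the plan says.** Protocol 10.5 covers three kinds of operational-research data: the cross-sectional quality-of-care surveys, the provider competency or knowledge assessments, and the caregiver and patient interviews. All are to be "analyzed using conventional statistical methods to compare means (t-tests or paired t-tests) or frequencies (chi-square tests) across intervention groups or time periods". It adds only that regression may be used to explore associations. It states no unit of analysis and does not mention the HF.

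Section 3.4.1 sets the survey design: 18 HFs, half from each arm, with "25 consecutive consultations with children aged 1 day to 14 years per HF, thus a total 450 HCW/child pairs". The survey is done three times. Of the comparisons over time it says: "Before-and-after intervention analysis will be performed between the baseline analysis and the phase 1 intervention arm HF". A second before-after comparison covers the control HFs once they receive ePOCT+ in Phase 2.

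The surveys also serve comparisons between arms. In the synopsis (Procedures and measurements) they are one of two data sources for secondary outcomes compared between intervention and control: "during a cross-sectional survey, observers in the consultation room will record key symptoms and signs assessed by HCWs". Section 7.1 lists among the Phase 1 secondary outcomes the percentage "of key symptoms and signs checked and diagnostic tests performed by HCWs".

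Section 10.3 specifies a multilevel logistic model with the cluster as a random effect for antibiotic prescription, then says: "Binary secondary outcomes will be evaluated in the same way". It goes on to require that every model allow for clustering and for the stratification factors.

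**The concern.** Section 3.1 justifies randomising facilities on the ground that HCWs are such that "their practices are influenced by the context of the HF they are working in". The same reasoning means that consultations within one HF resemble each other. Section 10.2 expects 75 HCWs using ePOCT+ in Phase 1. Over 20 intervention HFs that is 75/20 = 3.75 per HF, so 25 consecutive consultations come from a handful of clinicians. A chi-square test on pooled consultations treats the 225 per arm as independent.

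Between arms, confidence intervals would be too narrow, and differences in quality of care would be declared significant too often. This matters for Hypothesis 1.2 (improved quality of care). By the description in 8.1.7, control tablets record demographics and end-of-consultation decisions but not the signs examined. The between-arm comparison of signs checked therefore rests on these surveys.

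A reader also cannot tell which section governs. Section 10.3 requires cluster adjustment, but its heading names primary outcomes and its text reaches only binary secondary ones. Section 10.5 is the text specific to the surveys.

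**Working it through.** **Inputs.** From 3.4.1: 18 HFs, 9 per arm, m = 25 consultations per HF. This reproduces the stated total: 18 × 25 = 450, or 225 per arm. The two-sided 5% level is inferred from the 95% confidence intervals in 10.3, since 10.5 states none. No ICC is given for survey outcomes, so every ICC below is an assumption. Two values come from elsewhere in the documents: 0.002 for the clinical outcome (Protocol 10.1.1) and 0.08 for antibiotic prescription (SAP 3.2). The value 0.20 is 2.5 times the larger of these.

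**Between arms.**
- Design effect: DE = 1 + (25 − 1) × ICC.
- Actual error of an unadjusted nominal 5% test: 2 × [1 − Φ(1.96/√DE)].
- Unadjusted 95% CI half-width for the arm difference at a proportion of 50%: 1.96 × √(2 × 0.25/225) = 9.2 points.
- HF-level half-width, with 9 + 9 − 2 = 16 degrees of freedom: t(16) × √(2 × 0.25 × DE/225).

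| Assumed ICC | DE | Actual error | Simulated chi-square error | HF-level CI half-width (points) |
|---|---|---|---|---|
| 0.002 | 1.05 | 5.6% | 5.7% | 10.2 |
| 0.02 | 1.48 | 10.7% | 11.2% | 12.2 |
| 0.05 | 2.20 | 18.6% | 19.4% | 14.8 |
| 0.08 | 2.92 | 25.1% | 26.0% | 17.1 |
| 0.20 | 5.80 | 41.6% | 42.5% | 24.1 |

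The simulation drew beta-binomial data for 9 v 9 HFs of 25 consultations, with a true proportion of 50% in both arms and 20,000 replicates. In the same data, a t-test on the HF proportions kept its error between 4.9% and 5.4%. At ICC 0.08, the 225 consultations per arm carry the information of 225/2.92 ≈ 77.

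**Before-after in the same 9 HFs, unpaired consultation-level test.** Let c be the correlation of an HF's underlying level between two surveys. The variance of the difference, relative to what the test assumes, is 1 + 24 × ICC − 25 × ICC × c. At ICC 0.08 this equals 2.92 − 2c.

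| c | Variance factor | Actual error | Simulated error |
|---|---|---|---|
| 0 | 2.92 | 25.1% | 25.9% |
| 0.5 | 1.92 | 15.7% | 16.3% |
| 0.8 | 1.32 | 8.8% | 9.2% |
| 1 | 0.92 | 4.1% | 4.2% |

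A paired t-test on HF summaries kept its error between 4.9% and 5.1%.

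**The case against.** The strongest reply is that 10.5 is one generic sentence for three data types and never orders pooled consultation-level tests. It lists paired t-tests. Consultations with different children cannot be paired across surveys, so some recurring unit, HF or HCW, must be meant there. A t-test on HF summaries would satisfy the wording and be valid. This stands for means: there the fault is an unstated unit. It does not rescue chi-square tests for frequencies, which work on counts of consultations.

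A second reply is that if 10.3 governs survey-measured secondary outcomes, clustering is already handled, and if it does not, there is no contradiction, only an omission. In addition, the outcome on signs checked may be a score per consultation rather than binary. This also stands in part. The conflict is direct for binary secondary outcomes taken from the surveys. For scores, knowledge assessments and exit interviews it is a gap. Either way, a statistician following 10.5 would find no allowance for the HF. The optional regression sentence does not supply one, because it is exploratory and names no cluster term.

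Third, the size rests on a borrowed ICC. At 0.002 the inflation would be trivial. That value, however, is for the clinical outcome. Antibiotic prescription is a measure of HCW practice in the same project and is the closer analogue. Even an ICC of 0.02 roughly doubles the error.

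Fourth, 3.4.1 stresses change over time more than differences between arms, and for change over time the direction of the error is unknown. That is correct, but the comparison between arms is also planned.

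Finally, a separate Phase 1 SAP is cited and is not in the file. The SAP supplied covers only the medAL-mentor study, so whether the Phase 1 SAP settles the matter cannot be checked.

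**Conclusion.** The concern holds. As written, 10.5 permits, and for frequencies names, tests that ignore the randomised unit, and it disagrees with 10.3 for binary secondary outcomes measured in the surveys. Between arms at consultation level the tests are anti-conservative: about 25% error at an assumed ICC of 0.08, and from 5.6% to 42% over 0.002 to 0.20. Before-after, the error of an unpaired test at ICC 0.08 lies between 25% and 4.1%. It is too liberal if HF levels shift between surveys and slightly conservative if they are fully stable. These figures assume equal clusters of 25, as planned, and a two-sided 5% level. The damage is confined to secondary and operational-research results.

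**What to change.** Revise 10.5 to state, for the survey data:

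1. **Between arms:** use the multilevel model of 10.3 with an HF random effect, the stratification factors and a small-sample degrees-of-freedom correction for 18 HFs, or a t-test on the 18 HF-level summaries.
2. **Before-after:** pair by HF, with a paired t-test on HF summaries or a mixed model with HF and HF-by-survey random effects.
3. **Precedence:** say that these replace consultation-level t-tests and chi-square tests, so that 10.5 agrees with 10.3.

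Adjusting the Phase 1 comparison for each HF's own baseline survey value is optional and may gain precision.

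The change is to analysis wording and needs no new data. The price is wider between-arm intervals, from 10.2/9.2 ≈ 1.1 to 24.1/9.2 ≈ 2.6 times the unadjusted width over the assumed ICC range. Smaller differences in quality of care may then not reach significance.
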